3.4. Dose Adjustment Criteria

During the Extended Treatment Period, the investigator may reduce the dose of CBD or CBD placebo once from 40 mg/kg/day to 30 mg/kg/day for safety or tolerability. In addition, tapering of vigabatrin and CBD will be required as described in [Section 3.1.4](#).

3.5. Stopping Rules

The Investigator reserves the right to terminate the study in the interest of patient safety and welfare. The Sponsor reserves the right to terminate the study at any time for administrative reasons. Patients will also be discontinued when their liver enzymes and serum bilirubin reach:

- ALT or AST > 8 x ULN.
- ALT or AST > 5 x ULN for more than 2 weeks.
- ALT or AST > 3 x ULN and (TBL>2 x ULN or INR>1.5).
- ALT or AST > 3 x ULN with appearance of fatigue, nausea, vomiting, right upper quadrant pain or tenderness, fever, rash, and/or eosinophilia (> 5%).

4. TREATMENTS

4.1. Treatments Administered

4.1.1. Initial Treatment Period

On Day 1 (Visit 2), patients will receive the initial titration dose of vigabatrin (50 mg/kg/day divided twice daily [BID]), and either CBD 20 mg/kg/day plus matching CBD 20 mg/kg/day placebo or CBD 40 mg/kg/day placebo BID for 3 days.

Following the 3-day titration, on Day 4 (Visit 3) vigabatrin will be increased to 100 mg/kg/day [BID], and either CBD 30 mg/kg/day and matching CBD placebo 10/mg/kg/day or matching CBD 40 mg/kg/day placebo BID for 3 days.

On Day 7 (Visit 4) vigabatrin will be increased to 150 mg/kg/day plus CBD 40 mg/kg/day administered twice daily for the remaining 9 days. Placebo patients will receive CBD 40 mg/kg/day placebo BID for 15 days. All subjects will continue on their treatment at the end of study until confirmation from the central reader on the 24-hour video EEG and clinical laboratory results are received.

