1.3.3. Selected Clinical Safety Data

Insys study [INS011-14-029](#) enrolled 62 patients with refractory seizures between 1 and 17 years of age. Cannabidiol Oral Solution, 300 mg/mL at doses between 10 mg/kg/day and 40 mg/kg/day were generally well tolerated and no patient discontinued. Fifty-two of the 61 patients enrolled into a long-term safety study ([INS011-14-030](#)). Study INS011-14-030 was a long-term, open-label, 48-week study for pediatric patients aged 1 year to 17 years with refractory epilepsy who participated in the Phase 1/2 Study INS011-14-029.

Insys recently completed a long-term safety study (INS011-14-030) in pediatric patients with refractory epilepsy who participated in the Phase 1/2 PK study (INS011-14-029). This study was a long-term, open-label, 48-week study for pediatric subjects aged 1 year to 17 years with refractory epilepsy who participated in the Phase 1/2 Study INS011-14-029. A total of 52 subjects (9 infants, 26 children, and 17 adolescents) were enrolled and received at least one dose of the investigational product in this study. Forty-five (86.5%) subjects completed the study including follow-up. Seven (13.5%) subjects prematurely discontinued treatment and study participation: 2 (3.8%) subjects due to AEs, 3 (5.8%) subjects due to withdrawal of consent, 1 (1.9%) subject due to death considered not related to investigational product, and 1 (1.9%) subject due to other reason (reported lack of efficacy).

The mean modal dose (defined as the dose with the longest duration) was 24.42 mg/kg/day and the mean total duration of study drug was 311.1 days. Overall, 13 subjects (14.4%) had dose reductions during the study: 12 subjects (13.3%) had dose reductions due to an AE and 1 subject (1.1%) had a dose reduction due to “other” reason. The incidence of dose reductions resulting from an AE was higher for subjects who received 40 mg/kg/day (8 subjects, 30.8%) compared with subjects who received 20-<30 mg/kg/day (6 subjects, 8.8%) and 30-<40 mg/kg/day (1 subject, 6.6%). No subjects who received 10-<20 mg/kg/day and no infants had dose reductions. The trend was to increase the doses over the course of the study. There were 39 subjects (43.3%) who had dose increases during the study. The incidence of dose increases was higher for subjects who received 10-<20 mg/kg/day (14 subjects, 100%) compared with subjects who received 20-<30 mg/kg/day (16 subjects, 47.1%) and 30-<40 mg/kg/day (9 subjects, 56.3%).

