Patients will have a, minimum of a 9-hour video EEG that includes at least one full sleep-wake cycle during their Screening Visit to establish their baseline level of infantile spasms and hypsarrythmia and a 24-hour video EEG at Visit 5 (Day 14 to Day 15) of the Initial Treatment Period to establish their final level of infantile spasms and hypsarrythmia. A blinded central reader, not involved in the study, will evaluate the video EEGs and determine responder status. Details of the video EEG assessment will be provided in the video-EEG Charter. The treatment response categories are summarized in [Table 2](#). In addition, a 9-hour video EEG will be conducted during the Extended Treatment Period to confirm parent/caregiver report of relapse. If possible, a 9-hour video EEG will be conducted for patients who have continued into the Extended Treatment Period and decided to Early Withdraw. A video EEG is not required for patients who decide to withdraw during the Initial Treatment Period.

Table 2: Video EEG Response Definitions

Response Category	Definition
Complete Response	Complete resolution of spasms and hypsarrythmia confirmed by video EEG
Partial Response	Complete resolution of either spasms or hypsarrythmia confirmed by video EEG
Non-Response	No improvement or worsening of spasms/hypsarrythmia burden

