3.1.1. Initial Treatment Period

- Day 1 (Visit 2): Patients will receive the initial titration dose of vigabatrin (50 mg/kg/day divided twice daily [BID]), and either CBD 20 mg/kg/day plus matching CBD 20 mg/kg/day placebo or CBD 40 mg/kg/day placebo, each drug administered BID for 3 days.
- Day 4 (Visit 3): Patients will return to the study center to evaluate medical status (seizure diary, vital signs, and neurological exam), clinical laboratory assessments, concomitant medications, height/weight, and assess adverse events (AEs). For those patients who tolerate the initial dose, the dose for vigabatrin will be increased to 100 mg/kg/day BID, and either CBD 30 mg/kg/day and matching CBD placebo 10 mg/kg/day, or matching CBD 40 mg/kg/day BID placebo for 3 days.
- Day 7 (Visit 4): Patients will return to the study center to evaluate medical status (seizure diary, vital signs, and neurological exam), clinical laboratory assessments, concomitant medications, height/weight, and assess AEs. For those patients who tolerate the increased doses, the dose of vigabatrin will be increased to 150 mg/kg/day and CBD or CBD placebo to 40 mg/kg/day for the remaining 9 days. Vigabatrin, CBD, and matching placebo will be administered in a twice daily fashion at 12-hour intervals with meals.

As part of their standard of care, investigators will assess safety and tolerability of the treatment regimens throughout the study period. All subjects will continue on their treatment until confirmation from the central reader on the 24-hour video EEG and clinical laboratory results are received.

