8.2. Sample Size Determination

A total of 190 patients (130 and 60 patients in the two groups) will provide 80% power with a two-sided alpha of 0.05 to detect a difference in response rate, assuming the response with vigabatrin alone is 40% and the response with vigabatrin with Cannabidiol Oral Solution is 60%.

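### Dose escalation on Days 4 and 7 depends on tolerance in some protocol sections and not in others, no rule covers an infant who does not tolerate a step, and the Protocol and SAP would score that infant differently for the primary endpoint

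*Protocol*

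**What the plan says.** **Conditional text.** Protocol Section 3.1.1 says for Day 4: "For those patients who tolerate the initial dose, the dose for vigabatrin will be increased to 100 mg/kg/day BID". It puts the same condition on the Day 7 step. The synopsis (Initial Treatment Period) and footnote h of the Schedule of Events agree.

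**Unconditional text.** Section 4.1.1 reads "Following the 3-day titration, on Day 4 (Visit 3) vigabatrin will be increased to 100 mg/kg/day [BID"], and its Day 7 sentence has no tolerance condition either. The visit instructions in Sections 7.2.1.3 (Day 4) and 7.2.1.4 (Day 7) simply state the higher doses.

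**Dose adjustment.** Section 3.4 is limited to the later period: "During the Extended Treatment Period, the investigator may reduce the dose of CBD or CBD placebo once from 40 mg/kg/day to 30 mg/kg/day". Nothing equivalent exists for the Initial Treatment Period. Section 3.3 lists intolerable side effects among the reasons for which participation may be ended.

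**EEG after withdrawal.** Section 3.1: "A video EEG is not required for patients who decide to withdraw during the Initial Treatment Period". Section 7.2.5 restricts the withdrawal EEG to patients who reached the Extended Treatment Period. Section 3.3 encourages a 9-hour recording without that restriction, but the primary endpoint needs the 24-hour recording of Days 14 to 15.

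**Scoring.** Protocol 8.4.6 treats a patient with no Day 14-15 EEG as a non-responder. SAP 6.4.4 imputes nothing and analyses observed data. SAP 11.3, in the exposure section, says a patient with safety or tolerability problems counts as a treatment failure and is discontinued.

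**The concern.** Two problems meet in the same infant.

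The first is the dosing instruction. A site that follows Section 4.1.1 to the letter raises the dose in an infant whom Section 3.1.1 would not escalate. A site that follows Section 3.1.1 does not escalate, but finds no statement of what comes next. This bears on patient safety as well as on uniform conduct.

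The second is the endpoint. An infant held at the lower dose keeps the planned Day 14-15 EEG. An infant withdrawn has none. The two documents then give different answers on whether the withdrawn infant is a failure or is left out, and on whether the held infant is judged on the EEG or counted as a failure. Site practice and the choice of document could therefore decide a primary outcome that should rest on the central reader's EEG result. If intolerance is more frequent on CBD, the effect is not balanced between arms.

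**Working it through.** **1. The dosing texts side by side**

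| Place in Protocol | Day 4 step | Day 7 step |
|---|---|---|
| Synopsis | if tolerated | if tolerated |
| Schedule of Events, footnote h | if tolerated | if tolerated |
| 3.1.1 | if tolerated | if tolerated |
| 4.1.1 | no condition | no condition |
| 7.2.1.3 / 7.2.1.4 | no condition | no condition |
| 3.4 (dose adjustment) | not covered | not covered |

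**2. How one infant would be scored**

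| Route | Protocol 8.4.6 | SAP 6.4.4 | SAP 11.3 |
|---|---|---|---|
| Held, Day 14-15 EEG done | EEG result | EEG result | treatment failure, and discontinued |
| Withdrawn, no EEG | non-responder | not in observed data | treatment failure |

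SAP 11.3 does not say whether treatment failure means non-response for the primary endpoint.

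**3. What the scoring rule alone can do (illustration)**

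Assume that 10% of the 130 CBD infants (13) do not tolerate a step, and that response is 60% whether or not an infant tolerates the step and whichever route is taken.

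- Withdrawn, Protocol 8.4.6: responders = 0.60 × 117 = 70.2; rate = 70.2/130 = 54%.
- Withdrawn, SAP 6.4.4: 70.2/117 = 60%.
- Held with EEG, Protocol 8.4.6: 78/130 = 60%.
- Held with EEG, SAP 11.3 read as non-response: 70.2/130 = 54%.

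The same infants give a CBD rate that differs by 6 points, depending on the route and the text applied.

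**4. Power**

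Inputs from Protocol 8.2: "A total of 190 patients (130 and 60 patients in the two groups"), "assuming the response with vigabatrin alone is 40% and the response with vigabatrin with Cannabidiol Oral Solution is 60"%, two-sided alpha 0.05. The test is the chi-square test of Section 8.4.3.1.

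Plan's own figure first. Pooled rate = (60 × 0.40 + 130 × 0.60)/190 = 0.5368. Standard error under the null = √[0.5368 × 0.4632 × (1/60 + 1/130)] = 0.0778. Under the alternative = √(0.24/60 + 0.24/130) = 0.0765. Power = Φ[(0.20 − 1.96 × 0.0778)/0.0765] = Φ(0.62) = 73.3%. Exact enumeration of the chi-square test gives 73.0%. Section 8.2 says the trial "will provide 80% power with a two-sided alpha of 0.05 to detect a difference in response rate"; the 80% is not reproduced. That shortfall is a separate matter and is used here only as the starting value.

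Next, multiply each arm's rate by (1 − share lost and scored as non-response). The shares are assumptions, and lost infants are taken to respond otherwise at their arm's rate.

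| Lost, CBD / placebo | Rates | Exact power |
|---|---|---|
| 0 / 0 | 60% v 40% | 73% |
| 5% / 5% | 57% v 38% | 69% |
| 5% / 0 | 57% v 40% | 59% |
| 10% / 0 | 54% v 40% | 44% |

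**The case against.** **The conditional text may be enough.** The tolerance condition stands in three places, and Sections 4.1.1, 7.2.1.3 and 7.2.1.4 are silent on tolerance; none directs a site to escalate an infant who is not tolerating treatment. Many sites would read the documents together sensibly. That is fair, but the silent sections are the treatment and visit instructions, and even the conditional text stops short of saying what follows.

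**A reader might infer that withdrawal is the only way out.** The documents do not support this. Section 3.3 is permissive, and an infant who stays in the study without escalating still has the Day 14-15 EEG. The link from intolerance to discontinuation is explicit only in SAP 11.3.

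**A reader might infer from Section 1.3.3 that intolerance will be common.** There, dose reduction for adverse events was "higher for subjects who received 40 mg/kg/day (8 subjects, 30.8"%). That figure counts reductions, not withdrawals, in a 48-week study of patients aged 1 to 17 years. The next sentence reports no reductions in infants, and Section 4.4 repeats this for three studies. Two of 52 patients (3.8%) in the 48-week study stopped for adverse events. The reassurance has limits: that study had nine infants, and 0 of 9 has a one-sided 95% upper bound of 1 − 0.05^(1/9) = 28%. But 30.8% is not a basis for an expected loss here.

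**CBD-only loss is the unfavourable case.** Vigabatrin is raised on the same days in both arms, so some loss on placebo is likely too, and balanced loss costs less power. This stands.

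**Scoring intolerance as failure is a legitimate choice.** It is a choice of estimand. The objection to the present text is that the two documents do not make the same choice.

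**Conclusion.** The point holds as a contradiction and a gap. The Protocol states two escalation rules, has no provision for a Day 4 or Day 7 step that is not tolerated, and conflicts with SAP 6.4.4 and 11.3 on how that infant enters the primary analysis. Part of the SAP conflict probably arises because the SAP is written to Protocol V2.0 of 30 October 2017, which it describes with a different titration; that explains the mismatch but does not remove it.

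The size cannot be determined. The available text gives no early-withdrawal rate for infants, and Section 8.2 states no dropout allowance. The range of 69% to 44% power, against 73%, rests wholly on assumed losses of 5% to 10%, scored as non-response, in infants who would otherwise respond at their arm's rate. It shows that small shares matter; it does not predict a loss. A claim that handling would erase the treatment effect is not supported.

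**What to change.** 1. **Protocol.** Reconcile the synopsis, Schedule footnote h and Sections 3.1.1, 3.4, 4.1.1, 7.2.1.3 and 7.2.1.4 into one escalation rule, and have that rule also cover an infant who does not tolerate a step. Which rule applies is for the sponsor and its clinical advisers; none is proposed here.
2. **SAP.** Align Sections 6.4.4 and 11.3 with Protocol 8.4.6 so that an infant who does not tolerate a step is scored one way for the primary endpoint, whether or not a Day 14-15 EEG was obtained. State whether treatment failure in 11.3 means non-response.

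Requiring such infants to remain in the study to Day 15 is not part of this fix. It would have clinical consequences, because Section 4.7.2 prohibits new anti-epileptic therapies during the study, and the scoring conflict can be settled without it.

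The cost is wording in a protocol amendment, notice to sites, and a SAP revision that is due in any case to bring it to the current protocol. No added patients, visits or recordings are needed. The scoring decision should be made before unblinding.

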4.1.2. Extended Treatment Period

Following the Initial Treatment Period:

- Complete Responders will continue receiving their assigned treatments of vigabatrin plus either CBD 40 mg/kg/day or placebo for 75 days, until Week 13 (Day 90), to monitor progress for treatment response.
- During the Extended Treatment Period, the investigator may reduce the dose of CBD or CBD placebo to 30 mg/kg/day for safety or tolerability. If the subjects cannot tolerate the 30 mg/kg/day, the drug will be discontinued and the patient withdrawn from the study following the completion of the Taper Period.

4.1.3. Partial Responders

- Partial responders will be offered the opportunity to enroll in an open-label safety study that allows investigators to combine standard-of-care treatment with CBD.

4.1.4. Taper Period

Following the completion of the Initial Treatment Period (Visit 6), partial responders who do not enroll in the open-label safety study and non-responders will have vigabatrin and CBD or CBD placebo tapered as follows:

- Vigabatrin taper: 150 mg/kg/day will be reduced to 100 mg/kg/day for 3 days, then the 100 mg/kg/day dose will be reduced to 50 mg/kg/day for 3 days, and then discontinued.
- CBD or CBD Placebo taper: 40 mg/kg/day will be reduced to 30 mg/kg/day for three days, then 30 mg/kg/day will be reduced to 20 mg/kg/day for 3 days, and then discontinued.

Complete Responders will be tapered off vigabatrin and CBD or CBD placebo at the completion of the Extended Treatment Period, and all patients will be tapered off at any Early Withdrawal Visits, using the same schedules as described above. If the investigator decides to continue vigabatrin as a treatment for patients at the end of study or early withdrawal, tapering of vigabatrin will be left to the discretion of the PI.

CBD requires tapering off at the End of Study or at the Early Withdrawal visit.

4.2. Method of Assigning Patients to Treatment Groups

Following confirmation of eligibility, patients will be randomized into one of two investigational product dose groups (vigabatrin plus CBD 40 mg/kg/day or vigabatrin plus matching placebo).

The randomization schedule will be computer generated by using a permuted block algorithm and will randomly allocate the IP to randomization numbers. The randomization numbers will be provided to the drug packager who will prepare blinded drug kits. The randomization schedule will be prepared by the sponsor or sponsor's representative before the start of the study. No one involved in the study performance will have access to the randomization schedule before official unblinding of treatment assignment. No subject will be randomized into this study more than once.

4.3. Blinding and Unblinding Treatment Assignment

This is a double-blind study with vigabatrin, CBD, and matched CBD placebo components. Study centers will be provided with three dosage levels of CBD (20 mg/kg/day, 30 mg/kg/day, 40 mg/kg/day, and matching placebos) in identical packaging, and three dosage levels of vigabatrin (50 mg/kg/day, 100 mg/kg/day, and 150 mg/kg/day), matched with the randomization schedule for that center.

All patients and study personnel involved in the conduct of the study, including data management, will be blinded to the Initial Treatment Period.

Study personnel will endeavor to safeguard the integrity of the study blind to minimize bias in the conduct of the study. Treatment unblinding is discouraged if knowledge of the treatment assignment will not materially change the planned management of a medical emergency. Unblinding will be permitted in a medical emergency that requires immediate knowledge of the patient's treatment assignment. Unblinding should be discussed in advance with the sponsor, sponsor's representative, or medical monitor if possible. For emergency unblinding, study personnel will contact the sponsor or sponsor's representative. If the investigator is not able to discuss treatment unblinding in advance, then he or she must notify the sponsor, sponsor's representative, or medical monitor as soon as possible about the unblinding incident without revealing the patient's treatment assignment. The investigator or designee must record the date and reason for study unblinding in the source document for that patient. In all cases that are not emergencies, the investigator must discuss the event with the sponsor, sponsor's representative, and/or medical monitor prior to unblinding the patient's treatment assignment.

If the treatment assignment is unblinded for an individual patient, study personnel will be notified of that patient's treatment assignment without unblinding of the treatment assignments for the remaining patients in the study. Thus, the overall study blind will not be compromised. If a patient's treatment assignment is unblinded, he or she may or may not be asked to withdraw

from the study. The investigator will make this decision after consultation with the sponsor, sponsor's representative, or medical monitor.

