6. STUDY ASSESSMENTS

6.1. Efficacy Assessments

To assess the efficacy of Cannabidiol Oral Solution, a 9-hour video-EEG will be completed during Screening and a 24-hour video-EEG will be performed from Day 14 (Visit 5) to Day 15. During the Extended Treatment Period, a 9-hour video-EEG will be completed to confirm parent/caregiver reports of relapse or complete resolution. If possible, a 9-hour video EEG will be conducted for patients who have continued into the Extended Treatment Period and decided to Early Withdraw. A video EEG is not required for patients who decide to withdraw during the Initial Treatment Period.

The video EEGs should include at least one full wake/sleep cycle. Video EEGs may be first read by the investigator. However, no efficacy assessment will be made based on the investigator's reading of the video EEG and this read will not be captured in the database. An Independent Central Reader will evaluate all video EEGs in a blinded manner and determine responder status for the primary endpoint. Details regarding requirements for the conduction of the video EEG and the Independent Central Reader's review and assessment of the video EEG is outlined in the EEG Charter. The treatment response categories are summarized in [Table 2](#).

- The CGI-S will be completed by the investigator at screening.
- The CGI-I will be completed by the investigator at Visit 6 of the Initial Treatment Period, or the Early Withdrawal Visit.
- Daily seizure diaries will be completed throughout the Initial and Extended Treatment Periods, or the Early Withdrawal Visit.

If a patient discontinues the study prematurely, the investigator's impression of efficacy and tolerability of the study drug, as evaluated by CGI-I, will be assessed and recorded immediately before discontinuation. If possible, the parent/caregiver will be encouraged to have the patient have an Early Withdrawal video-EEG completed.

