8.1. Study Endpoints

8.1.1. Primary Efficacy Endpoint

The primary efficacy endpoint in this study is:

- Percent of patients who are considered complete responders, defined as complete resolution of spasms and hypsarrhythmia, confirmed by 24-hour video EEG from Day 14 to Day 15, as determined by the Independent Central Reader.

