8.4.6. Missing Data

There will be no imputation of the missing values. Patients without a video EEG assessment on Days 14-15 will be considered non-responders for all EEG-related endpoints. Percentage of spasm-free days will be calculated based on the number of entries (up to 15 days per measurement period). A sensitivity analysis may be conducted to assess the impact of the missing values on the final analysis. The sensitivity analyses will be detailed in the SAP.

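### After unblinding, an investigator who may know the arm decides without a criterion whether the infant leaves the study, and leaving before the Day 14-15 EEG settles or removes the primary outcome

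*Protocol*

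**What the plan says.** Protocol Section 4.3 discourages unblinding. It permits it in a medical emergency that needs the assignment, and requires prior discussion in all other cases. If a patient's "treatment assignment is unblinded, he or she may or may not be asked to withdraw" from the study. On who decides: "The investigator will make this decision after consultation with the sponsor, sponsor's representative, or medical monitor". No criterion is attached, and Section 3.3 does not name unblinding among the reasons for discontinuation.

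On who learns the arm, Section 4.3 states that "study personnel will be notified of that patient's treatment assignment without unblinding of the treatment assignments for the remaining patients in the study". When an emergency unblinding could not be discussed in advance, the sponsor side is told "as soon as possible about the unblinding incident without revealing the patient's treatment assignment".

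The primary endpoint (Protocol Section 8.1.1) is complete response "confirmed by 24-hour video EEG from Day 14 to Day 15, as determined by the Independent Central Reader". Protocol Section 6.1 adds: "A video EEG is not required for patients who decide to withdraw during the Initial Treatment Period". Section 7.2.5 limits the Early Withdrawal EEG to infants already in the Extended Treatment Period. Section 3.3 encourages one where possible, but it lasts 9 hours and is not the endpoint recording.

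The documents differ on a missing primary EEG. Protocol Section 8.4.6: "Patients without a video EEG assessment on Days 14-15 will be considered non-responders for all EEG-related endpoints". SAP Sections 6.4.4 and 9.7.1 plan no imputation and analyse observed data, with no non-responder rule. The primary tests also differ: chi-square in Protocol Section 8.4.3.1 and Fisher's exact test in SAP Section 10.6.1.

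**The concern.** The primary outcome is well protected for an infant who stays in the study, because a blinded central reader scores the recording whether or not the site knows the arm. Unblinding therefore gives no measurement reason to lose that outcome. Section 4.3 nevertheless opens a route around the protection. Someone who may know the arm can end participation without meeting any stated condition, no endpoint EEG is then required, and the missing EEG either becomes a non-response or removes the infant from the comparison.

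This is a discretionary withdrawal after randomisation, possibly made with the arm known. The intent-to-treat definition keeps the infant in the population but does not recover an unrecorded outcome. The effect can go either way: losing placebo responders inflates the apparent benefit, and losing CBD responders dilutes it. In the extension, withdrawal also ends relapse follow-up, although a 9-hour EEG is sought there if possible.

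**Working it through.** **The chain, step by step (Protocol).**
1. The infant is unblinded, and site personnel are told the arm (4.3).
2. The investigator decides on withdrawal; no criterion is given (4.3).
3. If this happens in the Initial Treatment Period, no EEG is required (6.1, 7.2.5).
4. No Day 14-15 EEG means non-responder (8.4.6). Under SAP 6.4.4 the infant has no observed outcome and is left out.

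**Inputs.** 130 CBD and 60 placebo infants; planned response 60% and 40%; two-sided alpha 0.05 (Protocol 8.2). Neither document gives an unblinding rate, so there is no plan figure to reproduce, and the tables below are illustrations.

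**Weight of one infant.** 1/130 = 0.8 percentage points in the CBD arm; 1/60 = 1.7 points in the placebo arm.

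**Formula.** Uncorrected chi-square = (p1 − p2)² / [p(1 − p)(1/130 + 1/60)], where p is the pooled rate and 1/130 + 1/60 = 0.02436.

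- 73/130 vs 25/60: difference 0.5615 − 0.4167 = 0.1449; p = 98/190 = 0.5158; standard error 0.0780; chi-square 3.45; p-value 0.063.
- 73/130 vs 24/60: difference 0.1615; p = 97/190 = 0.5105; standard error 0.0780; chi-square 4.29; p-value 0.038.

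**One would-be responder withdrawn, under each rule and test.**

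| Situation | Table | Chi-square p | Fisher p |
|---|---|---|---|
| Placebo responder stays | 73/130 vs 25/60 | 0.063 | 0.086 |
| Withdrawn, Protocol rule | 73/130 vs 24/60 | 0.038 | 0.043 |
| Withdrawn, SAP rule | 73/130 vs 24/59 | 0.049 | 0.060 |
| CBD responder stays | 72/130 vs 24/60 | 0.049 | 0.061 |
| Withdrawn, Protocol rule | 71/130 vs 24/60 | 0.061 | 0.086 |

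The placebo example crosses 0.05 under both tests with the Protocol rule. With the SAP rule it crosses under chi-square but not under Fisher, so the SAP's own combination of rule and test does not flip. The CBD example crosses only under chi-square; under Fisher it is non-significant throughout.

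**At the planned rates.** 0.60 × 130 = 78 and 0.40 × 60 = 24. 78/130 vs 24/60 gives chi-square p = 0.010 and Fisher p = 0.012. With CBD responders turned into non-responders one at a time, six losses (72/130) give chi-square p = 0.049 and seven (71/130) give 0.061. Under Fisher, significance goes at six (0.061).

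**Average effect, assumed range.** Suppose 1% to 5% of would-be placebo responders, and no CBD responders, are turned into non-responders. With true response 40% in both arms, the exact chi-square type I error goes from 4.96% to 4.98% (at 1%) and 5.67% (at 5%).

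**The case against.** The strongest reply is that the exposure is narrow. Unblinding is discouraged and must precede the Day 14-15 EEG to touch the primary endpoint. It changes a result only if the infant would have responded, and some of these infants would leave on Section 3.3 safety grounds anyway. Any binary endpoint can turn on one patient near 0.05. All of this stands and limits the size of the point, but it does not supply the missing criterion.

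Four stronger readings are tempting, and the documents do not support them.

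- *That the investigator and sponsor decide together, with the arm known.* The investigator decides and the sponsor side is consulted. After an emergency unblinding not discussed in advance, the sponsor side is notified without the arm.
- *That such withdrawals cannot be detected.* Section 4.3 requires the date and reason for unblinding in the source document. Section 3.3 requires prompt notice to the sponsor of a withdrawal. Protocol Section 8.4.1.1 and SAP Section 8 tabulate reasons by treatment group. What is lacking is a planned output that shows unblinding: the SAP's list of discontinuation reasons has no such category, so these cases could sit under investigator decision or other.
- *That data management is told the arm.* Section 4.3 mentions data management in a different sentence, on who is kept blind. The personnel to be notified are most naturally site staff. The wording is loose, no more.
- *That withdrawal always becomes a non-response.* That is the Protocol's rule only.

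**Conclusion.** The point holds in a limited form. As written, Section 4.3 lets an investigator who may know the arm decide, without a criterion, whether an unblinded infant stays. Withdrawal before the Day 14-15 EEG then fixes the primary outcome as non-response (Protocol) or removes the infant (SAP). The two rules must be reconciled; the SAP states that it is based on the protocol dated 30 October 2017.

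The likely effect is small. A reader might infer that one unblinded infant would decide this trial. That is true only close to the threshold, and it depends on the missing-data rule and the test. At the planned response rates, it takes seven lost CBD responders under chi-square, or six under Fisher. These figures assume that the infants concerned would have responded, and that unblinding is rare, which the documents suggest but do not quantify. This is a cheap improvement to make before such cases arise, because an endpoint EEG that was not recorded cannot be recovered. It is not evidence that the trial's result would be unreliable.

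**What to change.** 1. In Protocol Section 4.3, replace the open-ended withdrawal sentence with: *Unblinding is not in itself a reason for withdrawal from the study; unless consent is withdrawn, outcome follow-up continues and the Day 14-15 video-EEG is obtained and read by the blinded central reader.* Decisions on stopping treatment stay as they are in Section 3.3.
2. State that the assignment is disclosed only to staff who need it to treat that infant, in place of the general notification of study personnel.
3. Add a SAP listing of unblinded infants by arm, with date, reason and any later withdrawal.
4. Put one rule for a missing Day 14-15 EEG in both documents.
5. Do not add a sensitivity analysis that scores all unblinded infants as non-responders: those withdrawn already have that score under the Protocol, so it could not reveal selective withdrawal. If an analysis is wanted, vary the outcome of infants withdrawn after unblinding in both directions, by arm.

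Cost: two sentences in Section 4.3, one listing, and one aligned missing-data rule. The small downside is that a few CGI-I ratings will come from an unblinded investigator; these should be flagged.
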